6.2.1.3 SECONDARY OUTCOME ANALYSIS

All secondary analyses will be performed on an intention to treat basis using the primary analysis population as defined in section 4.3, utilising two-level models to allow for patients nested within sites.

Table 7 – Summary of secondary analyses

	Outcome	Analysis	Covariates
1	Time until initiation of IV antibiotic therapy	We will present the result as a groupwise boxplot with median and range of number of hours. Cox regression analysis will be used, with the results reported as hazard ratios (HR) and 95% confidence intervals. We will also produce a Kaplan Meier plot and cumulative incidence plot.	 a) Trial arm and baseline NEWS2 b) Trial arm, baseline NEWS2, age, number of comorbidities and gender

TPL/008/2(v1.0)

Canolfan Ymchwil Treialon

Short title: ISAP / SAP Template

2	Late IV antibiotic initiation – antibiotics commenced after 3 hours	We will report the groupwise frequency and percentage of late initiations. Logistic regression will be used, with the results reported as odds ratios (OR) and 95% confidence intervals.	a) b)	Trial arm and baseline NEWS2 Trial arm, baseline NEWS2, age, number of comorbidities and gender
3	Number of days on IV antibiotics (during admission) Number of days on IV antibiotics (total over the first 28 days)	We will present the result as a groupwise boxplot with median and range of number of days. Poisson regression analysis will be used, with results reported as incidence rate ratios (IRR) and 95% confidence intervals.	a) b)	Trial arm and baseline NEWS2 Trial arm, baseline NEWS2, age, number of comorbidities and gender
4	Number of days on any antibiotic (during admission) Number of days on any antibiotic (total over the first 28 days)	We will present the results as a groupwise boxplot with median and range of number of days. Poisson regression analysis will be used, with results reported as IRRs and 95% confidence intervals.	a) b)	Trial arm and baseline NEWS2 Trial arm, baseline NEWS2, age, number of comorbidities and gender
5	Number of days on broad- spectrum antibiotics (IV and oral) (during admission) Number of days on broad- spectrum antibiotics (IV and oral) (total over the first 28 days)	We will represent the result as a groupwise boxplot with median and range of number of days. Poisson regression analysis will be used, with results reported as IRRs and 95% confidence intervals.	a) b)	Trial arm and baseline NEWS2 Trial arm, baseline NEWS2, age, number of comorbidities and gender
6	Critical care admission (ICU or HDU) – at any point during admission	We will report the groupwise frequency and percentage of ICU and HDU admissions. Logistic regression will be used, with results reported as ORs and 95% confidence intervals.	a) b)	Trial arm and baseline NEWS2 Trial arm, baseline NEWS2, age, number of comorbidities and gender
7	Length of critical care stay (overnight stays)	We will represent the result as a groupwise boxplot with median and range of number of days. Poisson regression analysis will be used, with results reported as IRRs and 95% confidence intervals.	a) b)	Trial arm and baseline NEWS2 Trial arm, baseline NEWS2, age, number of comorbidities and gender

Canolfan Ymchwil Treialon

Short title: ISAP / SAP Template

8	Length of hospital stay (overnight stays)	We will represent the result as a groupwise boxplot with median and range of number of days. Poisson regression analysis will be used, with results reported as IRRs and 95% confidence intervals.	a) b)	Trial arm and baseline NEWS2 Trial arm, baseline NEWS2, age, number of comorbidities and gender
9	Adverse antibiotic outcomes	We will report the groupwise frequency and percentage of adverse outcomes events, overall and broken down by type of adverse event. Logistic regression will be used, with results reported as ORs and 95% confidence intervals.	a) b)	Trial arm and baseline NEWS2 Trial arm, baseline NEWS2, age, number of comorbidities and gender
10	Readmission to the hospital within 90 days	We will report the groupwise frequency and percentage of readmissions. Logistic regression will be used, with results reported as ORs and 95% confidence intervals.	a) b)	Trial arm and baseline NEWS2 Trial arm, baseline NEWS2, age, number of comorbidities and gender
11	Mortality within 90 days	We will report the groupwise frequency and percentage of deaths. Logistic regression will be used, with results reported as ORs and 95% confidence intervals.	a) b)	Trial arm and baseline NEWS2 Trial arm, baseline NEWS2, age, number of comorbidities and gender
	Mortality within 90 days – days until death	Additionally, we will represent the result as groupwise a boxplot with median and range of number of days until death. Cox regression analysis will be used, with results reported as HR and 95% confidence intervals. We will also produce a Kaplan Meier plot and a cumulative incidence plot.	a) b)	Trial arm and baseline NEWS2 Trial arm, baseline NEWS2, age, number of comorbidities and gender
12*	Health utility (EQ-5D-5L) at 28 days – summary index score (0-1)	We will report the mean (SD) of the score. A linear regression analysis will be used to test the difference between the groups.	a) b)	Trial arm and baseline NEWS2 Trial arm, baseline
	Health utility (EQ-5D-5L) at 28 days – visual analogue scale (VAS) (0-100)			NEWS2, age, number of comorbidities and gender
	Health utility (EQ-5D-5L) at 90 days - summary index score (0-1)			

TPL/008/2(v1.0)

Canolfan Ymchwil Treialon

Short title: ISAP / SAP Template

	Health utility (EQ-5D-5L) at	
	90 days – VAS (0-100)	

* For health utility (EQ-5D-5L) analyses, the current NICE guidelines suggest using the mapping function developed by van Hout et al. (2012). We will follow NICE guidelines at the time of analysis.

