3.3 SAMPLE SIZE

The sample size calculation was based on two co-primary outcomes:

1. 28-day mortality, for which we want to show non-inferiority of the PCT-guided assessment as compared to current standard practice, using an absolute 2.5% non-inferiority margin. Assuming 28-day mortality of 15% in patients managed as suspected sepsis treated in the ED, any increase in 28-day mortality from 15% to not more than 17.5% would be considered non-inferior. For 90% power and one-sided 5% significance level, the sample size required is 7002, assuming there is no difference in 28-day mortality between arms. Our patient focus group were also consulted on the 2.5% non-inferiority margin and felt that this was acceptable if there were mechanisms to monitor trial outcomes, and if this was what was needed to provide a sample size which would ensure the trial could be completed as well as answer the research question.

2. Initiation of antibiotic treatment, for which we want to show superiority. Currently, around 90% of patients managed as suspected sepsis receive antibiotics (Royal Liverpool and Broadgreen University Hospitals NHS Trust, unpublished data). Reducing this by 10 percentage points to 80% would be seen as a success. To detect such an effect with 90% power and a two-sided 5% significance level, the sample size required is 532, which is substantially lower than what is needed for the non-inferiority endpoint. With 7002 patients, we would be able to detect effects as small as a reduction from 90% to 87.6% prescriptions with 90% power.

Accounting for 5% dropout, a fixed-sample design would need a total sample size of 7372.

We planned to conduct one interim analysis (after 50% of patients provided data) with options to stop the trial early using group-sequential boundaries based on O'Brien-Fleming type alpha spending (O'Brien & Fleming, 1979, DeMets & Lan, 1994). We used a hierarchical approach (Figure 2) to recommend stopping for effectiveness if:

TPL/008/2(v1.0)

Canolfan Ymchwil Treialon

Short title:	ISAP / SAP Template
--------------	---------------------

- the PCT-guided assessment was non-inferior in terms of 28-day mortality and superior in terms of initiation of antibiotics, or
- the PCT-guided assessment was superior in terms of 28-day mortality (i.e., a significant reduction to less than 15%).

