6.2.4 ALTERNATIVE METHODS IF DISTRIBUTIONAL ASSUMPTIONS NOT MET

If the data does not meet the distributional assumptions of the analyses described above, variables will be transformed if possible. If transformations do not improve the distributions, the model choice may vary from what is described above. For example, if the effect of baseline NEWS2 is distinctly nonlinear we may account for it using higher-order terms or splines. If the number of days on antibiotics/in critical care do not meet the Poisson regression assumption that the variance is equal to the mean, we may use negative binomial or quasi-Poisson models to account for the overdispersion. A time interaction term may be added to Cox regression if the proportional hazards assumption is not met. Additionally, if the proportional hazards assumption is not met, we may consider restricted mean survival analysis, or possibly the Fine-Gray model if the assumption is badly violated. If censoring is an issue, rather than using boxplots, we will use the median and centiles from the survival distribution. Any changes will be fully documented.

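### The default boxplots for time to IV antibiotics and time to death describe only patients who had the event; make all-participant summaries the default instead

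*SAP*

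**What the plan says.** SAP section 6.2.1.3, Table 7, fixes the default descriptive display for two time-to-event outcomes. Row 1, time until IV antibiotic therapy: "We will present the result as a groupwise boxplot with median and range of number of hours". Row 11, time until death within 90 days: "we will represent the result as groupwise a boxplot with median and range of number of days until death". Both rows add a Cox hazard ratio with a 95% interval, a Kaplan-Meier plot and a cumulative incidence plot. Row 11 also gives the frequency and percentage of deaths and a logistic odds ratio.

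Section 6.2.4 holds a conditional replacement: "If censoring is an issue, rather than using boxplots, we will use the median and centiles from the survival distribution". It gives no criterion for when this applies. The assumption checks named in section 6.2.3 are proportional hazards, overdispersion and non-linearity of NEWS2; none of them concerns censoring.

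**The concern.** Hours to IV exist only for patients given IV, and days until death only for patients who died. Each boxplot and its median therefore compares arms within a group formed after randomisation by the outcome itself. For IV antibiotics, that is a group the intervention is meant to shrink. Section 6.2.1.3 announces all secondary analyses as intention to treat; this display is not a comparison of the randomised groups.

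The section 6.2.4 condition leaves the choice of display until the data have been seen. Yet the planning figures already settle it: with 15% dead at day 28, about 85% have no death time at that point, and at 80% to 90% receiving antibiotics, 10% to 20% have no start time. The risk is that a reader compares two medians in hours or days and draws a conclusion that the whole randomised groups do not support.

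**Working it through.** **Inputs from SAP section 3.3.** "Assuming 28-day mortality of 15% in patients managed as suspected sepsis treated in the ED"; a margin stated as "using an absolute 2.5% non-inferiority margin"; "For 90% power and one-sided 5% significance level, the sample size required is 7002"; "around 90% of patients managed as suspected sepsis receive antibiotics"; "Reducing this by 10 percentage points to 80% would be seen as a success".

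**The plan's own figures.**
- Mortality: n per arm = (1.645 + 1.282)² × 2 × 0.15 × 0.85 / 0.025² gives 3495, total 6990 against the stated 7002 (0.2% apart).
- Antibiotics, 90% v 80%, two-sided 5%, 90% power, pooled variance under the null: 266 per arm, total 532, as stated.

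The planning rates are therefore read correctly.

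**Time to IV antibiotics.** Assumptions, not in the SAP: 90% and 80% are the shares ever given IV; times among those given IV are lognormal with median 2 h and SD 0.8 on the log scale; the 10 points who avoid IV are spread evenly over start times. A participant never given IV counts as not reached.
- Treated-only median: 2.00 h in both arms.
- The all-participant median is the 0.5/0.9 = 55.6th centile of the starters' distribution in control and the 0.5/0.8 = 62.5th in the intervention arm.
- Control: 2 × exp(0.8 × 0.1397) = 2.24 h. Intervention: 2 × exp(0.8 × 0.3186) = 2.58 h.
- Range: with SD 0.4 the pair is 2 × exp(0.4 × 0.1397) = 2.11 and 2 × exp(0.4 × 0.3186) = 2.27 h; with SD 1.2 it is 2 × exp(1.2 × 0.1397) = 2.37 and 2 × exp(1.2 × 0.3186) = 2.93 h.

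The unchanged treated-only median and the move from the 55.6th to the 62.5th centile do not depend on the lognormal shape. Only the size in hours does.

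**Time to death.** Assumptions: 15% dead at day 28 in both arms, so the early hazard is h = −ln(0.85)/28 = 0.00580 per day; after day 28 the hazard is 0.5h in control and 0.25h in the intervention arm.
- Control: F(90) = 1 − 0.85 × exp(−0.5h × 62) = 29.0%. Half of that, 14.5%, is reached at −ln(1 − 0.145)/h = 27.0 days.
- Intervention: F(90) = 1 − 0.85 × exp(−0.25h × 62) = 22.3%. Half, 11.2%, is reached at 20.4 days.

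The arm with fewer deaths shows the shorter median among decedents. Raising the late hazard to 0.75h instead gives 35.1% dead and a median of 35.0 days: more deaths, longer median. Under proportional hazards (HR 0.75 or 1.25) the direction is right, but the median moves little: about 0.6 day if the control late hazard is 0.5h (27.6 and 26.4 against 27.0), and about 1.4 days if it is h (40.6 and 37.8 against 39.2).

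**Would the section 6.2.4 replacement work?** For IV, yes: with 80% to 90% starting, the all-participant median exists. For death, the SAP gives no 90-day mortality, so an assumption is needed. With constant hazard, F(90) = 1 − 0.85^(90/28) = 40.7%, and the median would fall at ln 2/h, about day 119. From 12% or 17.5% at day 28, F(90) is 33.7% or 46.1%. Reaching 50% by day 90 needs 28-day mortality of at least 1 − 0.5^(28/90) = 19.4%, or a hazard after day 28 of 1.47 times the earlier one. Lower centiles exist: on the constant hazard, 5% are dead at day 8.8 and 10% at day 18.2.

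**The case against.** The strongest reply is that nothing inferential rests on these boxplots. Both outcomes are secondary; effectiveness is judged from the co-primaries in Table 3; dummy Table A3 shows only a hazard ratio for either outcome, plus an odds ratio for 90-day death. The Kaplan-Meier and cumulative incidence plots and the percentage dead stand beside the boxplot. The 3-hour share is itself co-primary, and late initiation is row 2. Section 6.2.4 already names the remedy. All of this stands, and it is why the point is minor. It does not turn an event-only median into a comparison of randomised groups.

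Three stronger readings are tempting and are not supported.
- A reader might infer that the section 6.2.4 fallback fails for death, or itself points the wrong way. An unreached median is uninformative but has no direction; the fallback offers centiles as well; and whether the median is reached depends on an unstated hazard after day 28.
- A reader might infer that treated-only times would make treatment look faster. This does happen if the avoided 10 points are the slowest starters: the treated-only median falls to 1.79 h with the all-participant median fixed at 2.24 h. But those patients start after about 5.3 h, so the share started by 3 hours is 0.9 × 0.694, about 62%, in both arms. That scenario implies no effect on the co-primary and does not represent the plan's target.
- A reader might take these medians for headline results. The SAP gives them no such standing.

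The death example is also a constructed case: equal early mortality with a different late hazard. It shows that reversal is possible, not that it is likely.

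**Conclusion.** The concern holds as a minor defect of descriptive reporting. The default displays in rows 1 and 11 condition on having the event, and their replacement hangs on an undefined trigger although event-free patients are certain from the planning rates. For IV, the treated-only median can hide a rise in the all-participant median from 2.2 to 2.6 h (2.1 to 2.3 h, or 2.4 to 2.9 h, at the other spreads tried), assuming even avoidance and reading the SAP's 90% and 80% as shares ever given IV. For death, the decedent median can reverse direction under non-proportional hazards and barely moves under proportional ones. That the survival median is not reached by day 90 is probable, resting on a constant or falling hazard after day 28. The co-primary analyses, hazard ratios and curves are untouched.

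**What to change.** Make the survival-distribution summary the default in Table 7 and delete the condition on censoring in section 6.2.4.
- **Row 1:** report the median and centiles of time to IV over all participants in the analysis population, keeping those never given IV in the denominator. Label any boxplot *among those given IV only*.
- **Row 11:** drop the boxplot of days until death. Report Kaplan-Meier survival, or cumulative incidence, at days 28 and 90 by arm with the difference and its interval, or prespecified lower centiles that can be estimated.

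The cost is wording plus a few numbers read from curves already planned; no new data are needed. Since the deviation log records analyses from 24/06/24 to 09/12/24, a change made now should be entered there as a reporting choice made after analysis, not presented as prespecified.

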6.2.2 COVARIATE ADJUSTMENT

Other covariates of potential interest, including age, comorbidities and gender, will be adjusted for in secondary analyses together with minimisation factors. Subgroup analyses are described in section 6.2.6.

6.2.3 ASSUMPTION CHECKING

Modelling and distributional assumptions will be checked prior to analysis and reporting. Specifically, time-to-event models will be tested for the proportional hazard assumption, Poisson regression models will be assessed for overdispersion and baseline NEWS2 score will be assessed for non-linearity.

6.2.4 ALTERNATIVE METHODS IF DISTRIBUTIONAL ASSUMPTIONS NOT MET

If the data does not meet the distributional assumptions of the analyses described above, variables will be transformed if possible. If transformations do not improve the distributions, the model choice may vary from what is described above. For example, if the effect of baseline NEWS2 is distinctly nonlinear we may account for it using higher-order terms or splines. If the number of days on antibiotics/in critical care do not meet the Poisson regression assumption that the variance is equal to the mean, we may use negative binomial or quasi-Poisson models to account for the overdispersion. A time interaction term may be added to Cox regression if the proportional hazards assumption is not met. Additionally, if the proportional hazards assumption is not met, we may consider restricted mean survival analysis, or possibly the Fine-Gray model if the assumption is badly violated. If censoring is an issue, rather than using boxplots, we will use the median and centiles from the survival distribution. Any changes will be fully documented.

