- Poisson regression analysis of days on IV/any abx in first 14 days
- Logistic regression analysis of whether IV abx was initiated within 12 hours

TPL/008/2(v1.0)

Canolfan Ymchwil Treialon

Short title: IS

: ISAP / SAP Template

- Logistic regression analysis of whether IV abx was initiated within 7-days
- Descriptive summaries of the following, to explore whether the treatment pathway may have changed between the arms
 - \circ ~ Time from triage (+/- randomization) to prescription of antibiotics
 - \circ ~ Time from triage (+/- randomization) to administration of antibiotics
 - \circ \quad Time between prescription and administration of antibiotics
 - \circ ~~ % blood cultures taken in first 24 hours (No other measure in CRF)
 - Broad spectrum Abx (Watch/Reserve) vs narrow spectrum (Access)
 - Initial Diagnosis Infection vs Not Infection
 - Cause of Death
 - Time to HDU/ITU admission
 - Broad spectrum Abx (Watch/Reserve) vs narrow spectrum (Access)
 - Abx choice Compare distribution of No Antibiotics> PO>IV Narrow>IV broad
 - % Microbiology tests in first 24 hours (Blood cultures only)
 - % Microbiology tests in first 24 hours (Any)
 - \circ ~~ % Any antimicrobial resistance detected, if yes which by %
 - Duration of antibiotics (initial course started within 24 hours of attendance)
 - Length of hospital stay
 - o % No antibiotics vs any antibiotics
 - % Late course of antibiotics (2-28 days)
 - Time to late antibiotics
 - % Readmitted to hospital
- Descriptive summary of the days on no abx, oral, iv broad, iv narrow, combination for each NEWS score and arm

05/09/24

- Tabulate first prescription within 24 hours from triage by arm
- Tabulate arm by final diagnosis with mortality in the cells infection vs non infection
- Tabulate deaths in withdrawals by arm

19/09/24

- Tabulate 28-day mortality in different algorithm adherence groups including the discordant groups (low clinical risk & high algorithm risk and vice versa) (unexpected vs expected PCT result)
- A logistic regression analysis of trial arm's effect on being alive and not readmitted at 90 days
- Subgroup analysis (as described in section 6.2.6) of grading of clinician conducting assessment
- Subgroup analysis (as described in section 6.2.6) of index of deprivation decile
- Tabulate time between 1st and 2nd assessment overall, by arm and by NEWS2
- Time series plot of ED crowding by site

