8.1.2 Secondary outcomes

Table A3 – Secondary outcome analysis results

	Outcome	Analysis	Treatment effect estimate [95% CI]	p-value
1	Time until initiation of IV antibiotic therapy ^(a)	Primary	HR =	
		Adjusted for covariates	HR =	
2	Late IV antibiotic initiation – antibiotics commenced after 3	Primary	OR =	
	hours ^(b)	Adjusted for covariates	OR =	

TPL/008/2(v1.0)

Canolfan Ymchwil Treialon

Short title: ISAP / SAP Template

		1	I I
3	Number of days on IV antibiotics (during admission) ^(a)	Primary	IRR =
		Adjusted for covariates	IRR =
	Number of days on IV antibiotics $(1 + 1)^{(2)}$	Primary	IRR =
	(total over first 28 days) ^(a)	Adjusted for covariates	IRR =
4	Number of days on any antibiotic	Primary	IRR =
	(during admission) ^(a)	Adjusted for covariates	IRR =
	Number of days on any antibiotic	Primary	IRR =
	(total over first 28 days) ^(a)	Adjusted for covariates	IRR =
5	Number of days on broad-	Primary	IRR =
	spectrum antibiotics (IV and oral) (during admission) ^(a)	Adjusted for covariates	IRR =
	Number of days on broad-	Primary	IRR =
	spectrum antibiotics (IV and oral) (total over the first 28 days) ^(a)	Adjusted for covariates	IRR =
6	ICU or HDU admission – at any	Primary	OR =
	point during admission ^(b)	Adjusted for covariates	OR =
7	Length of ICU/HDU stay ^(a)	Primary	IRR =
		Adjusted for covariates	IRR =
8	Length of hospital stay ^(a)	Primary	IRR =
		Adjusted for covariates	IRR =
9	Adverse antibiotic outcomes ^(b)	Primary	OR =
		Adjusted for covariates	OR =
10	Readmission to the hospital	Primary	OR =
	within 90 days ^(b)	Adjusted for covariates	OR =
11	Mortality within 90 days ^(b)	Primary	OR =
		Adjusted for covariates	OR =
	Mortality within 90 days - time	Primary	HR =
	until death ^(a)	Adjusted for covariates	HR =
12	Health utility (EQ-5D-5L) at 28	Primary	MD =
	days ^(c)	Adjusted for covariates	MD =
		Primary	MD =

Canolfan Ymchwil Treialon

Short title: ISAP / SAP Template

	Health utility (EQ-5D-5L) at 28 days ^(c)	Adjusted for covariates	MD =
	Health utility (EQ-5D-5L) at 90	Primary	MD =
	days ^(c)	Adjusted for covariates	MD =
	Health utility (EQ-5D-5L) at 90	Primary	MD =
	days ^(c)	Adjusted for covariates	MD =
Analys	onfidence interval, HR = hazard ratio, Ol sis method: (a) cox regression, (b) logist iates in all models: baseline NEWS2.		

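### Eight secondary day counts rest on Poisson regression whose fallback puts transformation first, leaves the overdispersion remedy optional and does not name hospital stay

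*SAP*

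**What the plan says.** SAP section 6.2.1.3 (Table 7) prescribes the same model for every day count. For IV antibiotic days: "Poisson regression analysis will be used, with results reported as incidence rate ratios (IRR) and 95% confidence intervals". Rows 4, 5, 7 and 8 say the same: "Poisson regression analysis will be used, with results reported as IRRs and 95% confidence intervals". Rows 3, 4 and 5 each cover two windows (admission, and the first 28 days), and rows 7 and 8 cover critical care and hospital nights, so there are 2 + 2 + 2 + 1 + 1 = 8 outcomes. All secondary analyses are done "utilising two-level models to allow for patients nested within sites".

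Section 6.2.3 commits to examining the Poisson models for overdispersion before analysis and reporting. It names no statistic and no threshold.

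Section 6.2.4 gives the consequences. Its opening rule, for all models, is: "variables will be transformed if possible. If transformations do not improve the distributions, the model choice may vary from what is described above". A later example concerns antibiotic days and critical care days whose variance does not equal their mean: "we may use negative binomial or quasi-Poisson models to account for the overdispersion". Hospital stay is not named there. Any change is to be documented.

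In section 8.1.2, the day-count rows of dummy Table A3 carry the marker (a) and an IRR cell. The note under the table reads "method: (a) cox regression".

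**The concern.** Poisson standard errors assume that the variance equals the mean. Day counts in a mixed emergency population rarely behave that way: some patients have zero days, most have a few, and some have many. The planned site level absorbs variation between sites, but not the spread between patients within a site.

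The check will therefore probably fail, and the fallback becomes the working analysis plan. As written, its one firm step (*will*) is the wrong one for a count. A log transform is undefined at zero days. With an added constant, or with a square root, the arm effect is no longer a ratio of mean days, which is what Tables 7 and A3 promise. Nor does a transformed outcome in a Poisson model have variance equal to its mean. The steps that would work are discretionary (*may*), have no trigger, and are not stated for hospital nights.

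The trial is open-label, and these outcomes describe whether antibiotic exposure and bed use changed. The variance model, and possibly the effect measure, should not be left to choice once the data are seen.

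**Working it through.** **Plan's own figure.** The SAP gives no mean, SD, dispersion or power for any day count, so there is nothing to reproduce. Every mean and SD below is an assumption.

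**Formula.** Let Var(Y) = phi × mean. The correct standard error of the log IRR is sqrt(phi) times the Poisson one. The true size of a nominal two-sided 5% Poisson test is 2 × [1 − Φ(1.96/sqrt(phi))].

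| phi | Interval should be wider by | True size | Coverage |
|---|---|---|---|
| 2 | 1.41 | 16.6% | 83.4% |
| 4 | 2.00 | 32.7% | 67.3% |
| 6 | 2.45 | 42.4% | 57.6% |
| 9 | 3.00 | 51.4% | 48.6% |
| 16 | 4.00 | 62.4% | 37.6% |

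**Is overdispersion likely?** SAP section 3.3 puts antibiotic receipt at about 90%, with 80% as the target. Suppose the other 10% to 20% have zero days and treated patients' days are exactly Poisson with mean mu. Then phi = 1 + (proportion of zeros) × mu. For mu of 5 to 7 days (assumed), phi runs from 1 + 0.1 × 5 = 1.5 to 1 + 0.2 × 7 = 2.4, and the true size from 11% to 21%. That is before any real difference in duration between treated patients. For critical care, if 5% are admitted for a mean of 4 nights (assumed), phi = 1 + 0.95 × 4 = 4.8 and the size is about 37%.

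**Assumed means and SDs**, with phi = SD²/mean:

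| Outcome | Mean/SD | phi | sqrt(phi) |
|---|---|---|---|
| Antibiotic days | 3/3 | 3.0 | 1.7 |
| Antibiotic days | 4/4 | 4.0 | 2.0 |
| Antibiotic days | 4/5 | 6.25 | 2.5 |
| Antibiotic days | 8/7 | 6.1 | 2.5 |
| Hospital nights | 7/8 | 9.1 | 3.0 |
| Hospital nights | 8/12 | 18 | 4.2 |
| Critical care nights | 0.3/1.8 | 10.8 | 3.3 |

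**On the IRR scale.** Take 7002 patients (SAP section 3.3), so 3501 per arm, mean 4, no effect, and ignore covariates. The Poisson SE is sqrt(2/(3501 × 4)) = 0.0120, giving a 95% interval of 0.977 to 1.024. With SD 5 the SE is 0.0120 × 2.5 = 0.0299, giving 0.943 to 1.060.

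**Simulation check.** 7002 patients, 20 sites (assumed), negative binomial counts, NEWS2 in the model, no true effect, 200 runs per scenario. Site was fitted as fixed effects, as a stand-in for the random intercept.

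| Mean/SD | Poisson errors: rejections | Quasi-Poisson errors: rejections |
|---|---|---|
| 4/4, capped at 28 days | 34.5% | 5.5% |
| 4/5, capped at 28 days | 44% | 3.5% |
| 7/8 | 53% | 5% |
| 8/12 | 65% | 3.5% |
| 0.3/1.8 | 57% | 5% |

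The Monte Carlo SE at 5% is sqrt(0.05 × 0.95/200) = 1.5 percentage points, so the last column is compatible with 5%. Accounting for site did not remove the excess rejections; correcting for dispersion did.

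**The case against.** The SAP foresaw the problem. Section 6.2.3 makes the overdispersion check firm and applies it to all Poisson models, hospital stay included. Section 6.2.4 names two sound remedies, and quasi-Poisson keeps both the mean model and the IRR. Its transformation sentence is generic, and the count-specific sentence goes straight to the alternative models, so a sensible analyst might never transform a count. Only secondary outcomes are involved. All of this stands, and it limits the point to the order of the steps, the missing trigger, the word *may* and the unnamed hospital stay.

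Three stronger readings are tempting, and the document does not support them:

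- A reader might infer that the reported intervals will be several times too narrow. That needs Poisson errors to be kept after a failed check, and it rests on SDs the SAP does not give. For antibiotic days the scenarios tried reach only about 2.5.
- A reader might infer from the (a) marker in Table A3 that a Cox analysis of day counts is also planned. The same rows call for IRRs, and the footnote is damaged in the text available. This is at most a label slip.
- A reader might take the deviation log's "Poisson regression analysis of days on IV/any abx in first 14 days" as proof that the remedy was skipped. The entry does not say which standard errors were used.

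**Conclusion.** The point holds as a defect in the fallback rule, not as a missing method. Followed literally, section 6.2.4 tries the unsuitable remedy first and leaves the suitable one optional, without a criterion and without naming hospital stay.

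If Poisson errors were kept, intervals would be too narrow by sqrt(phi): about 1.7 to 2.5 times for antibiotic days and 3 to 4 times for critical care and hospital nights. These factors depend entirely on the assumed means and SDs. That phi exceeds 1 is much safer, since zeros alone push it above 1. The co-primary outcomes are analysed by logistic regression, and the effectiveness decision in SAP Table 3 uses no day count, so the trial's main conclusion is not touched. This should be changed, but it is not critical.

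**What to change.** For rows 3, 4, 5, 7 and 8 of Table 7, with hospital stay named explicitly:

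- Make an overdispersion-robust model the default from the start. Use either a two-level negative binomial, or a Poisson mean model with robust standard errors that still accounts for site. Choose one and state it.
- Report the IRR as a ratio of mean days.
- State in section 6.2.4 that count outcomes are not transformed.
- Correct the (a) label on these rows in Table A3.

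If the analyses are already done, state which standard errors were used, and re-report the intervals where they were uncorrected Poisson errors. The cost is a few lines of SAP text, a small change in the code, and wider intervals where the data are overdispersed.
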